## 1.2 Purpose

The purpose of the study is to evaluate the efficacy, safety and tolerability of LIK066 in T2DM patients with cardiac disease and HF to help inform decisions on further development of LIK066.

# 2 Study objectives and endpoints

## 2.1 Primary objective

[figure not shown]
To determine the dose-response signal and assess the dose-response relationship of LIK066 2.5mg, 10mg, and 50mg qd as measured by the change from baseline (BL) in NT-proBNP relative to placebo after 12 weeks of treatment in T2DM patients with HF.

## 2.2 Secondary objectives

1. To evaluate the effect of all LIK066 doses *vs* placebo at 12 weeks and 36 weeks on:
  - Change from BL in glycated hemoglobin (HbA1c), see [Section 6.4.6](#).
  - Change from BL in fasting plasma glucose (FPG), see [Section 6.4.7](#).
  - Change from BL in weight, see [Section 6.4.1](#).
  - Change from BL in body composition (bio-impedance in all patients where appropriate and dual-energy x-ray absorptiometry (DXA) in a subset of patients, see [Section 6.4.3](#))
  - Change from BL in sitting systolic blood pressure (SBP) and diastolic blood pressure (DBP), see [Section 6.4.8](#).
  - Change from BL in the fasting lipid profile and hsCRP, see [Section 6.4.9](#).
  - Change from BL in 24h urinary glucose and sodium excretion, in a subset of patients, see [Section 6.4.10](#).
  - Change from BL in left atrial size and volume assessed by echocardiography, see [Section 6.4.5](#).
  - Change from BL in NYHA class, see [Section 6.4.4](#).
2. To evaluate the effect of all LIK066 doses *vs* empagliflozin at 12 weeks and 36 weeks on:
  - Change from BL in HbA1c, see [Section 6.4.6](#).
  - Change from BL in FPG, see [Section 6.4.7](#).
  - Change from BL in weight, see [Section 6.4.1](#).
  - Change from BL in body composition (bio-impedance in all patients where appropriate and DXA in a subset of patients, see [Section 6.4.3](#))
  - Change from BL in sitting SBP and diastolic blood pressure (DBP), see [Section 6.4.8](#).
  - Change from BL in the fasting lipid profile and hsCRP, see [Section 6.4.9](#).

- Change from BL in 24h urinary glucose and sodium excretion, in a subset of patients (see [Section 6.4.10](#)).

3. To evaluate the change from BL to 36 weeks in all LIK066 doses *vs* placebo on NT-proBNP.
4. To evaluate safety (adverse events (AEs) and lab parameters) and tolerability of LIK066 over 12 weeks and over 36 weeks for all patients (see [Section 6.5](#))
5. To evaluate 24h urinary calcium and phosphate excretion after 12 weeks and after 36 weeks in a subset of patients (see [Section 6.4.10](#)).
6. To evaluate bone mineral density in a subset of patients (see [Section 6.5.5](#))

## 3      **Investigational plan**

### 3.1      **Study design**

[figure not shown]
This is a multi-center, randomized, double-blind, double-dummy, parallel-group study evaluating the efficacy, safety and tolerability of 3 doses of LIK066 *vs* placebo and *vs* empagliflozin.

**Pre-Screening:** Pre-screening for some blood tests is possible (it is optional) and can be used to identify appropriate patients to be screened for this clinical study. The pre-screening visit includes blood tests for NT-proBNP, HbA1c, eGFR and serum potassium, which will be analyzed at the central laboratory. At Visit 1, these laboratory parameters will be assessed by the central laboratory, independently whether or not pre-screening was done for the patient.

#### 3.1.1      **Epoch 1 (screening)**

Patients will be screened at Visit 1 (see [Figure 3-1](#)). The screening period (Epoch1) takes approximately 2 weeks. Patients meeting all eligibility criteria will enter the run-in Epoch 2 at Visit 101. If patients fail to meet one or more inclusion/exclusion criteria, they can be re-screened once. If for technical reasons (e.g. hemolyzed blood sample, broken or lost tube) laboratory results are not definable, such parameters can be re-tested.

### Figure 3-1 Study design

#### 3.1.2 Epoch 2 (placebo run-in)

Patients meeting the eligibility criteria defined in [Section 4](#) will enter the placebo run-in (Epoch 2). During the approximately 2 weeks duration of Epoch 2, patients will receive single-blind placebo run-in medication as described in [Section 5.2](#).

At Visit 101, the patients' volume status must be assessed based on physical examination and laboratory values and, if hypovolemic, corrected during the run-in.

#### 3.1.3 Epoch 3 (treatment)

After the placebo run-in Epoch 2, eligible patients will be randomized in a 1:1:2:2:2 ratio to one of the following regimens at Visit 201 (randomization), see [Section 5.2](#):

- LIK066 2.5mg qd at bedtime
- LIK066 10mg qd at bedtime
- LIK066 50mg qd at bedtime
- Empagliflozin (up-titrated from 10mg qd to 25mg qd after 2 weeks); in the morning
- Placebo LIK066 at bedtime/Placebo Empagliflozin in the morning

At randomization, patients must be stratified based on geographical region and the left ventricular ejection fraction (LVEF) measurement at Visit 101: < 45% versus  $\geq 45\%$ . Only if the LVEF results from the central reading vendor are not available in time for randomization, the LVEF result from Visit 101 read locally by a cardiologist or from the last measurement (echocardiogram, nuclear study, or left ventricular angiography) done locally prior to enrollment into the study can be used for stratification.

Following randomization, patients will attend study visits in Epoch 3 (12 weeks) for the evaluation of the short-term efficacy (change in NT-proBNP), tolerability and safety parameters as defined in [Table 6-1](#). During Epoch 3, patients will take the study medication as described in [Section 5.5.4](#).

### **Treatment of T2DM**

Patients will continue their usual T2DM treatment. Patients taking sulfonylureas (SU) or insulin may be at an increased risk of hypoglycemia when LIK066 or empagliflozin is added, therefore reduction of the dose of the SU or insulin should be considered:

- A reduction by 50%, or as close to 50% as possible based on dose options available locally, of the dose of SUs for patients (see [Section 5.5.3](#)) using such medication (either as monotherapy or in combination with other oral anti-diabetic drugs (OADs)) should be considered. In case of persistent deterioration in glycemic control, the concomitant background OAD should be initially escalated to the maximal approved dose, followed by addition of rescue medication when required (see [Section 5.5.6](#)). To limit the number of patients with early deterioration of glycemic control who would meet the FPG rescue criteria early after randomization (see [Section 5.5.6](#)) an FPG randomization criterion is included in [Section 4.2](#).
- For patients on insulin, initial dose reduction of the total daily insulin dose by 10% or more should be considered at the investigator's discretion based on patient's total daily dose and glycemic control. Due to the potential risk of ketoacidosis with SGLT2i, dose reduction in patients with  $\text{HbA1c} \geq 8\%$  may not be appropriate. In case of deterioration in glycemic control (see [Section 5.5.6](#)), insulin can be up-titrated.

#### **3.1.4      Epoch 4 (treatment)**

After completing the procedures required at the last study visit of Epoch 3 (Visit 301) patients will continue in Epoch 4 the treatment they were allocated to in Epoch 3 for 24 weeks. Long-term efficacy (assessed by HbA1c, echocardiography and NT-proBNP), tolerability and safety parameters as defined in [Table 6-1](#) will be evaluated.

[figure not shown]
### **3.2      Rationale for study design**

The study is designed as a standard randomized, controlled, parallel-group study. A single-blind placebo run-in epoch (Epoch 2) is included to familiarize patients with the study drug intake schedule and correct hypovolemia (if diagnosed at Visit 101). The effect on NT-proBNP will be evaluated after 12 weeks of treatment in Epoch 3, as well as after 36 weeks of the study (Epoch 4) to provide information about the longer-term effect of LIK066 on NT-proBNP, and on clinical and echocardiography parameters. Glycemic control will also be assessed after 12 and 36 weeks of treatment.

[figure not shown]
The patient population is described in more detail in [Section 4](#) below.

### 3.3 Rationale for dose/regimen, route of administration and duration of treatment

LIK066 has been studied in multiple clinical trials with a variety of dosing regimens using either single or multiple daily doses at durations of up to 12 week in healthy subjects, patients with T2DM and obese patients.

Since the objective is to find a dose with sub-optimal to optimal effect on SGLT1 and SGLT2 inhibition in the kidney, but with no or minimal gut effect to minimize the risk of diarrhea, LIK066 50mg qd is selected as the highest dose for this study.

To minimize the risk of GI adverse effects of the SGLT1 inhibition in the gut such as diarrhea, the LIK066 dose will not be taken around mealtime; hence dose administration is recommended at bedtime. The 10mg dose is selected between the low and top dose in the study and to enable exploration of the shape of the dose-response curve.

Based on results from previous exploratory phase II studies in HF comparing sacubitril/valsartan with valsartan (e.g. LCZ696B2214; [Solomon et al, 2012](#)), treatment with LIK066 for a duration of 12 weeks would be expected to be sufficient in order to reveal a significant change in NT-proBNP. Twelve weeks after introducing an anti-diabetic treatment is an accepted time point for initial evaluation of drugs' effect on glycemic control (HbA1c). The full duration of exposure of 36 weeks will provide data for parameters requiring longer follow-up to be evaluated (echocardiography) as well as safety data.

### 3.4 Rationale for choice of comparator

[figure not shown]
A placebo group is included to obtain efficacy, tolerability and safety data in an unbiased manner and to determine the dose-response characteristics of the investigational drug. An active comparator empagliflozin, which is approved in the treatment of T2DM to improve glycemic control, is included as a reference drug ([Zinman et al, 2015](#)). Empagliflozin has also shown CV benefit in T2DM patients in the EMPA-REG Outcome study. Considering that the mechanism leading to the CV benefit with empagliflozin currently remains unclear, the higher of the two approved doses in patients with T2DM, empagliflozin 25mg qd, was chosen as a comparator to potentially achieve a maximum effect on NT-proBNP. Choosing the higher of the two doses should not pose a safety concern, as no difference in the safety profile of empagliflozin 10 mg and 25 mg was reported in the EMPA REG Outcome study in patients with eGFR  $\geq 30$  ml/min/1.73m^2 ([Fitchett et al, 2016](#)), a cut-off value lower than the 45 ml/min/1.73m^2 in CLIK066B2204. In order to minimize potential adverse effects empagliflozin will be up-titrated from 10mg qd to 25mg qd after 2 weeks of treatment.

### **3.5 Purpose and timing of interim analysis**

No interim analysis is planned.

### **3.6 Risks and benefits**

The risk to patients in this study will be minimized by compliance with the eligibility criteria and study procedures, and close clinical monitoring.

Further information is provided in the Investigator Brochure (IB).

Publications on SGLT2 inhibition in subjects with T2DM treated with selective SGLT2 inhibitors reported higher incidences of urinary tract infections (UTIs) and genital mycotic infections compared with placebo (Bailey et al, 2010; Nauck et al, 2011; Nyirjesy et al, 2012) and some genital infections have been seen in healthy volunteers and patients treated with LIK066. SGLT2 inhibition may result in hypotension in elderly subjects, in subjects with low blood systolic pressure, or if on diuretics, ACE inhibitors, or ARBs. Patients with T2DM treated with antidiabetic agents, especially with sulphonylurea or insulin, may be at an increased risk of hypoglycemia. In rare cases treatment with SGLT2 inhibitors may be complicated by ketoacidosis (Rosenstock et al, 2015). However, this has not been seen to date in clinical studies with LIK066. In long-term clinical studies in patients with T2DM with CVD or at high risk for CVD, an increase in cases of lower limb amputation (primarily of the toe) has been observed with the SGLT-2 inhibitor canagliflozin (Neal et al, 2017). No lower limb amputations have been seen in LIK066 studies to date, but since this risk may constitute a possible class effect, patients with a higher risk for amputation events should be instructed on routine preventative foot care and maintaining adequate hydration. The only preclinical/class safety issues which have been seen in clinical studies with LIK066 are the GI side effects and vulvovaginal infections. A detailed description of safety in humans with LIK066 is found in the LIK066 IB.

Hematology and biochemistry tests will be monitored at each study visit after randomization and study drug can be discontinued for clinically significant laboratory change or abnormality as per investigator's judgment. Detailed criteria for follow-up in case of a liver event are defined in [Appendix 2](#). To prevent UTIs and genital infections, patients will be instructed to pay attention to genital hygiene and have appropriate hydration. If UTI and/or genital infections occur, treatment will be initiated as appropriate at the investigator's discretion.

Strict criteria for deterioration of glycemic control and initiation of rescue anti-diabetic medication are provided ([Section 5.5.6](#)). To minimize the risk of hypoglycemia when study drug is added to patients treated with SUs or insulin, guidance is provided in [Section 3.1.3](#). Considering the potential benefit patients with T2DM and mild and moderate renal impairment may have on their risk of CV death and HF hospitalization ([Section 1.1](#)) patients with eGFR down to 45 ml/min/1.73m^2 are included in this study. No safety concern in addition to the known adverse effects of SGLT2i has been reported in the EMPA REG Outcome study which included patients with T2DM with eGFR down to 30 ml/min/1.73m^2 ([Zinmann et al, 2015](#)).

This clinical study involves exposure to radiation from DXA total body and bone scans in a subset of patients. The total amount of radiation exposure per patient from these scans will be equivalent to less than 30 days of exposure to natural background radiation. For effective radiation doses at this level the risk for the patient is considered to be minimal. Therefore, the radiation exposure in this study involves minimal risk and is necessary to obtain the research information desired ([Stabin, 2016](#)).

Benefits to participation in the study may include blood glucose reduction, weight reduction and, potentially, improvement in HF signs and symptoms, as well as in some cardio-metabolic markers such as NT-proBNP, blood pressure or lipids.

## 4 Population

The study population will consist of male and female patients ( $\geq 18$  years old) with type 2 diabetes and heart failure (heart failure with preserved ejection fraction (HFpEF) and heart failure with reduced ejection fraction (HFrEF)). The goal is to randomize a total of approximately 496 patients in approximately 140 centers worldwide. Since a 25% screening failure rate and a 33% run-in failure rate is expected, approximately 1000 patients will be screened.

### 4.1 Inclusion criteria

Patients eligible for inclusion in this study must fulfill all of the following criteria:

1. Written informed consent must be obtained before any assessment is performed.
2. Male or female outpatients,  $\geq 18$  years of age at Visit 1.
3.  $\text{BMI} \geq 22 \text{ kg/m}^2$  at Visit 1.
4. Type 2 diabetes with  $\text{HbA1c}$  between 6.5% and 10.0% at Visit 1.
5. Documented symptomatic chronic heart failure (NYHA II-IV) with at least one of the following symptoms at the time of Visit 1:
  - Dyspnea on exertion
  - Orthopnea
  - Paroxysmal nocturnal dyspnea
  - Peripheral edema
6. Plasma NT-proBNP  $> 300 \text{ pg/ml}$  at Visit 1.
7. Patients receiving ACEi, ARBs, MRAs, ARNi and/or  $\beta$ -blockers must be on a stable dose of these medications during the 1 month period prior to Visit 1.
8. Patients must be on diuretic therapy prior to Visit 1 (flexible dosing is permitted).
9. Controlled systolic BP defined as a target systolic BP less than 140mmHg; systolic BP up to and including 160mmHg if patient is on three or more medications to control BP, at randomization (Visit 201).
10.  $\text{eGFR} \geq 45 \text{ ml/min/1.73m}^2$  at Visit 1 (calculated by the Modification of Diet in Renal Disease formula (MDRD)).
11. Serum potassium  $\leq 5.3 \text{ mM}$  at Visit 1.

### 4.2 Exclusion criteria

Patients fulfilling any of the following criteria are not eligible for inclusion in this study. No additional exclusions may be applied by the investigator, in order to ensure that the study population will be representative of all eligible patients.

1. Use of other investigational drugs within 5 half-lives of Visit 1, or within 30 days, whichever is longer.

2. History of hypersensitivity to any of the study drugs or their excipients or to drugs of similar chemical classes.
3. Diagnosis of electrocardiogram (ECG) abnormalities indicating significant risk of safety for patients participating in the study such as:
  - Concomitant clinically significant cardiac arrhythmias, e.g., sustained ventricular tachycardia, and clinically significant second or third degree AV -block without a pacemaker.
  - History of familial long QT syndrome or known family history of torsades de pointes.
  - Atrial fibrillation with a resting heart rate >100 beats per minute (bpm) at Visit 1.
4. Patients taking medications prohibited by the protocol (see [Section 5.5.8](#))
5. History of malignancy of any organ system (other than localized basal cell carcinoma of the skin or *in situ* cervical cancer), treated or untreated, within the past 5 years, regardless of whether there is evidence of local recurrence or metastases.
6. Pregnant or nursing (lactating) women.
7. Women of child-bearing potential, defined as all women physiologically capable of becoming pregnant, unless they are using basic methods of contraception during dosing of investigational drug. Basic contraception methods include:
  - Total abstinence (when this is in line with the preferred and usual lifestyle of the patient). Periodic abstinence (e.g., calendar, ovulation, symptothermal, post-ovulation methods) and withdrawal are not acceptable methods of contraception.
  - Female sterilization (have had surgical bilateral oophorectomy with or without hysterectomy), total hysterectomy or tubal ligation at least six weeks before taking investigational drug. In case of oophorectomy alone, only when the reproductive status of the woman has been confirmed by follow up hormone level assessment.
  - Male sterilization (at least 6 months prior to screening). For female patients on the study, the vasectomized male partner should be the sole partner for that patient.
  - Barrier methods of contraception: condom or occlusive cap (diaphragm or cervical/vault caps). For UK: with spermicidal foam/gel/film/cream/vaginal suppository.
  - Use of oral, (estrogen and progesterone), injected or implanted hormonal methods of contraception or other forms of hormonal contraception that have comparable efficacy (failure rate <1%), for example hormone vaginal ring or transdermal hormone contraception or placement of an intrauterine device (IUD) or intrauterine system (IUS).

In case of use of oral contraception women should have been stable on the same pill for a minimum of 3 months before taking investigational drug.

Women are considered post-menopausal and not of child bearing potential if they have had 12 months of natural (spontaneous) amenorrhea with an appropriate clinical profile (e.g. age appropriate, history of vasomotor symptoms) or have had surgical bilateral oophorectomy (with or without hysterectomy), total hysterectomy or tubal ligation at least six weeks ago. In the case of oophorectomy alone, only when the reproductive status of the woman has been confirmed by follow up hormone level assessment is she considered not of child bearing potential.

If the above wording is not in line with specific country regulations, exclusion criteria for women of child-bearing potential will be managed locally and in line with those regulations.

8. Type 1 diabetes, monogenic diabetes, diabetes resulting from pancreatic injury, or secondary forms of diabetes (e.g. Cushing's syndrome or acromegaly-associated diabetes).
9. Use of SGLT2 inhibitors within 2 months of Visit 1, or between Visit 1 and Visit 201 (randomization).
10. Self-measured FPG > 12.2mM (220mg/dL) on two occasions in the week prior to randomization (Visit 201).
11. History of ketoacidosis, lactic acidosis, or hyperosmolar coma, or any of these occurring between Visit 1 and Visit 201 (randomization).
12. Symptomatic genital infection or UTI in the 4 weeks prior to Visit 1, or between Visit 1 and Visit 201 (randomization).
13. GI disorders associated with chronic diarrhea.
14. Myocardial infarction (MI), stroke, surgery for heart disease, percutaneous coronary intervention (PCI) in the 3 months prior to Visit 201 (randomization).
15. Unstable angina within 3 months of Visit 1, or between Visit 1 and Visit 201 (randomization).
16. Isolated right HF due to pulmonary disease.
17. Dyspnea and/or edema from non-cardiac causes, such as lung disease, anemia, or severe obesity.
18. Hemodynamically significant mitral and/or aortic valve disease.
19. Hemodynamically significant obstructive lesions of left ventricular outflow tract, including aortic stenosis.
20. Hypertrophic obstructive cardiomyopathy.
21. Secondary forms of cardiomyopathy such as restrictive cardiomyopathy or infiltrative cardiomyopathy (e.g., amyloid disease).
22. Patients with a history of any organ transplant or who were on a transplant list (life expectancy < 6 months at time of entry into the study).
23. Patients with a mean sitting systolic blood pressure  $\leq$  100mmHg, at Visit 201 (randomization).
24. Patients with an implantable medical device (e.g. cardioverter defibrillator (ICD)) that has discharged in the month prior to Visit 1.
25. Episode(s) of malignant ventricular tachycardia or any other types of severe arrhythmia producing significant hemodynamic consequences or considered life-threatening within 3 months of Visit 1.

26. Acute or chronic liver disease (except liver steatosis), such as hepatitis, cirrhosis or portal hypertension at Visit 1 or Visit 201 (randomization).
27. History of hepatitis B or C, or Hepatitis A or B vaccination in the last 3 months prior to Visit 1, or between Visit 1 and Visit 201 (randomization).
28. Active substance abuse, alcohol abuse (as defined by consumption of more than 24 alcohol units per week) and alcohol related history of disease within the past 2 years.
29. Chronic treatment with medication which has a hepatotoxic potential.
30. Chronic use of anti-retroviral therapies.
31. Chronic use of strong CYP3A4 inhibitors (e.g. clarithromycin, telithromycin, itraconazole, ketoconazole, voriconazole or posaconazole) or chronic use of strong uridine-5'-diphosphoglucuronosyltransferase (UGT) inhibitors (e.g. probenecid, valproic acid or mefenamic acid).
32. Concurrent medical condition that may interfere with the interpretation of efficacy and safety data.
33. Clinically significant thyroid stimulation hormone (TSH) level outside of the normal range at Visit 1.
34. Alanine aminotransferase (ALT), or aspartate aminotransferase (AST) more than three-fold above upper limit of normal ( $>3 \times \text{ULN}$ ), or total bilirubin/direct bilirubin  $> 1.5 \times \text{ULN}$  at Visit 1, confirmed by repeat measurement within 5 working days of the respective visit.
35. Hemoglobin  $< 11\text{g/dL}$  in men,  $< 10\text{g/dL}$  in women at Visit 1 (screening).
36. Platelet count  $< 100,000/\mu\text{l}$  and/or white blood cell (WBC) count  $< 4000/\mu\text{l}$  at Visit 1 (screening).
37. Hematuria determined by dipstick measurement at Visit 1 (screening).
38. Elevated fasting triglycerides (TG)  $> 5.6\text{mM}$  (500mg/dl), at Visit 1 (screening), confirmed by repeat measurement within 3 working days of the respective visit.
39. Clinically significant laboratory abnormalities which, in the opinion of the investigator, cause the patient to be considered inappropriate for inclusion in the study.
40. History of lower limb amputation (including toe amputation), or if occurring between Visit 1 and Visit 201 (randomization).
41. Diabetic foot ulcer at Visit 1, or between Visit 1 and Visit 201 (randomization).

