## 14 Appendix 2: Liver event and Laboratory trigger Definitions and Follow-up Requirements

**Table 14-1 Liver Event and Laboratory Trigger Definitions**

	Definition/ threshold
LIVER LABORATORY TRIGGERS	
 
• <math>3 \times \text{ULN} < \text{ALT} / \text{AST} \leq 5 \times \text{ULN}</math>
 
• <math>1.5 \times \text{ULN} < \text{TBL} \leq 2 \times \text{ULN}</math>
 

LIVER EVENTS	
 
• <math>\text{ALT or AST} > 5 \times \text{ULN}</math>
 
• <math>\text{ALP} > 2 \times \text{ULN}</math> (in the absence of known bone pathology)
 
• <math>\text{TBL} > 2 \times \text{ULN}</math> (in the absence of known Gilbert syndrome)
 
• <math>\text{ALT or AST} > 3 \times \text{ULN}</math> and <math>\text{INR} > 1.5</math>
 
• Potential Hy's Law cases (defined as <math>\text{ALT or AST} > 3 \times \text{ULN}</math> and <math>\text{TBL} > 2 \times \text{ULN}</math> [mainly conjugated fraction] without notable increase in ALP to <math>> 2 \times \text{ULN}</math>)
 
• Any clinical event of jaundice (or equivalent term)
 
• <math>\text{ALT or AST} > 3 \times \text{ULN}</math> accompanied by (general) malaise, fatigue, abdominal pain, nausea, or vomiting, or rash with eosinophilia
 
• Any adverse event potentially indicative of a liver toxicity*
 

\*These events cover the following: hepatic failure, fibrosis and cirrhosis, and other liver damage-related conditions; the non-infectious hepatitis; the benign, malignant and unspecified liver neoplasms

TBL: total bilirubin; ULN: upper limit of normal

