2.6.2.5 ECG

The following variables will be descriptively summarized by visit and treatment: QTcF duration (msec), heart rate (beats/min), PR duration (msec), RR duration (msec), and QRS duration (msec).

The number and percentage of patients meeting the following criteria will be summarized by visit and treatment group for the double-blind period:

- QTcF > 500 msec
- QTcF > 480 msec
- QTcF > 450 msec
- QTcF increases from baseline \geq 30 msec
- QTcF increases from baseline \geq 60 msec
- PR > 200 and \leq 220 msec
- PR > 220 msec
- PR increases from baseline > 25% (PR > 200 msec)
- QRS > 110 and \leq 120 msec
- QRS > 120 msec
- QRS changes from baseline > 25 % (QRS > 110 msec)
- Heart rate > 100 beats/min
- Heart rate < 50 beats/min

In addition, a visit-based shift table will be provided to summarize the shifting from BL for each ECG parameter.

Cutoff points below are used to define normal or abnormal criteria in the above ECG shift table:

- QTcF: >450 or $=<$ 450 msec for male, or, >460 or $=<$ 460 msec for female
- QRS: >120 or $=<$ 120 msec
- PR: >200 or $=<$ 200 msec
- HR: >100 or $=<$ 100 beats/min

A listing of ECG parameters together with newly occurring or worsening abnormalities will be provided.

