2.6.2.6 Liver events

The liver event and laboratory trigger definitions are specified in the Appendix 2 of the study protocol. Liver event data will be listed.

The number and percentage of patients who meet the liver toxicity criteria in [Table 2-7](#) post baseline will be summarized by treatment group for the double-blind period. Listings of patients with clinically notable LFT values will be provided.

Table 2-7 Criteria for evaluating liver toxicity

Parameter	Criterion
ALT or AST	ALT or AST > 3xULN ALT or AST > 5xULN ALT or AST > 8xULN ALT or AST > 10xULN
Hy's category	ALT or AST >3x ULN and TBL >1.5x ULN ALT or AST > 3xULN & TBL > 2xULN ALT or AST > 5xULN & TBL > 2xULN ALT or AST > 8xULN & TBL > 2xULN ALT or AST > 10xULN & TBL > 2xULN ALT or AST > 3xULN & TBL > 2xULN & ALP ≤ 2xULN
TBL&ALP	TBL >1.5x ULN and ALP >2x ULN TBL >2x ULN and ALP >2x ULN
Isolated TBL	TBL >1.5x ULN & ALT and AST ≤3x ULN and ALP ≤2x ULN TBL >2x ULN & ALT and AST ≤3x ULN and ALP ≤2x ULN TBL >3x ULN & ALT and AST ≤3x ULN and ALP ≤2x ULN
Isolated ALP	ALP >1.5x ULN & ALT and AST ≤3x ULN and TBL ≤1.5x ULN ALP >2x ULN & ALT and AST ≤3x ULN and TBL ≤1.5x ULN ALP >3x ULN & ALT and AST ≤3x ULN and TBL ≤1.5x ULN ALP >5x ULN & ALT and AST ≤3x ULN and TBL ≤1.5x ULN

ALP: alkaline phosphatase; ALT: alanine aminotransferase; AST: aspartate aminotransferase; TBL: total bilirubin; ULN: upper limit of normal.

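### The isolated-ALP rows of SAP Table 2-7 and the QTcF >480 and >500 msec rows do not separate abnormalities present at entry from new ones

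*Protocol*

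**What the plan says.** **Entry.** Protocol 4.2, criterion 34, excludes patients with "Alanine aminotransferase (ALT), or aspartate aminotransferase (AST) more than three-fold above upper limit of normal", or with total or direct bilirubin above 1.5 times ULN, at Visit 1. The finding has to be "confirmed by repeat measurement within 5 working days of the respective visit". ALP is not in this criterion, and none of the 41 exclusion criteria gives it a limit. Criterion 3 covers ECG abnormalities, including "clinically significant second or third degree AV -block without a pacemaker" and long-QT history, but sets no numeric limit on QTcF.

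**Liver summary.** SAP 2.6.2.6 says that the number and percentage of patients meeting the liver toxicity criteria in Table 2-7 "post baseline will be summarized by treatment group for the double-blind period". The lowest isolated-ALP row is "ALP >1.5x ULN & ALT and AST ≤3x ULN and TBL ≤1.5x ULN"; the others use 2, 3 and 5 times ULN.

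**ECG summary.** SAP 2.6.2.5 says: "The number and percentage of patients meeting the following criteria will be summarized by visit and treatment group for the double-blind period". The list includes QTcF above 450, 480 and 500 msec.

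SAP 2.1.1 defines baseline as the last measurement before or at randomization. Neither counting rule refers to it for these rows.

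**The concern.** A threshold count is useful as a safety signal when it shows patients who crossed the threshold on treatment. Where entry places no ceiling on the parameter and the count ignores the baseline value, the row mixes stable, pre-existing abnormalities with new ones. The title of Table 2-7 presents its rows as liver toxicity criteria, so someone reading the ALP rows would naturally take them as on-treatment findings.

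At stake is how readable these rows are. Background cases raise the count in every arm and pull the ratio between arms towards one, so a real excess is harder to see.

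**Working it through.** The plan states no figure on this point, so there is none to reproduce. The check compares thresholds and then gives a hypothetical size.

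**1. Which liver rows are exposed?**

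| Table 2-7 rows | Lowest cut-off | Entry limit at Visit 1 | Exposed? |
|---|---|---|---|
| ALT or AST | >3 × ULN | >3 × ULN excluded | Only unconfirmed values, or rises between Visit 1 and randomization |
| Hy's category | ALT/AST >3 × ULN with TBL >1.5 × ULN | Both limited | As above |
| TBL & ALP; isolated TBL | TBL >1.5 × ULN | >1.5 × ULN excluded | As above |
| Isolated ALP | >1.5 × ULN | None | Yes |

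The structural gap is therefore the four isolated-ALP rows. The absolute QTcF rows have no numeric entry limit either.

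**2. Do other planned outputs isolate new onset at these thresholds?**

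- Laboratory shift tables (SAP 2.6.2.3.1) use low, normal and high. ALP of 1.1 and 1.7 × ULN are both high.
- SAP Table 2-4 flags ALP only for an increase above 100%. A new rise from 0.8 to 1.55 × ULN is (1.55 − 0.8)/0.8 = 94%, so it is not flagged there. It enters Table 2-7 together with stable carry-over.
- The QTcF shift table is cut at 450 msec (men) and 460 msec (women). A patient already above that cut who then passes 480 msec appears as abnormal at both times.
- The QTcF rows for increases of at least 30 and 60 msec are not combined with the 480 or 500 msec thresholds. A rise of less than 30 msec that crosses 480 msec is not in them.
- The listing of newly occurring or worsening ECG abnormalities is not a count by arm.

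**3. Size under assumed carry-over.** Let q be the share of patients who meet the threshold at baseline and still meet it afterwards. The documents give no value, so a range is shown. Assumed new-onset risks are 3% (active) and 1% (placebo).

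Shown risk = q + (1 − q) × new-onset risk.

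- q = 2%: active 0.02 + 0.98 × 0.03 = 4.94%; placebo 0.02 + 0.98 × 0.01 = 2.98%; ratio 1.66; difference 1.96 points.
- q = 5%: active 0.05 + 0.95 × 0.03 = 7.85%; placebo 0.05 + 0.95 × 0.01 = 5.95%; ratio 1.32; difference 1.90 points.

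| q | Ratio shown | Difference (points) | Carry-over patients of 62 | Carry-over patients of 124 |
|---|---|---|---|---|
| 0 | 3.00 | 2.0 | 0 | 0 |
| 1% | 1.99 | 1.98 | 0.6 | 1.2 |
| 2% | 1.66 | 1.96 | 1.2 | 2.5 |
| 5% | 1.32 | 1.90 | 3.1 | 6.2 |
| 10% | 1.17 | 1.80 | 6.2 | 12.4 |

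The last two columns are n × q for the planned arm sizes. The chance of at least one carried-over patient, 1 − (1 − q)^n, is 71% (n = 62) and 92% (n = 124) at q = 2%, and 96% and 99.8% at q = 5%.

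**The case against.** The strongest reply is that these are descriptive tables in a randomized trial with a placebo arm, and that the SAP already plans baseline-referenced outputs. A patient with a stable ALP of 1.7 × ULN would appear as high-to-high in the shift table and would be absent from the Table 2-4 ALP row. Carry-over is equal across arms in expectation, and the risk difference hardly moves. Table 2-7 is reported as numbers and percentages, not ratios. Criterion 26 ("Acute or chronic liver disease (except liver steatosis), such as hepatitis, cirrhosis or portal hypertension at Visit 1 or Visit 201") and the investigator's discretion under criterion 39 will also keep out some patients with raised ALP. All of this stands and limits the size of the problem. It does not remove it, because no planned table by arm shows new onset at the ALP multiples or at 480 and 500 msec.

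A reader might also draw three stronger conclusions that the documents do not support:

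- *The whole liver table is contaminated.* Criterion 34 matches the lowest ALT/AST and bilirubin cut-offs.
- *The SAP has discarded the protocol's qualifiers, such as "in the absence of known bone pathology" for ALP or known Gilbert syndrome for bilirubin.* SAP 2.6.2.6 refers to protocol Appendix 2 for the definition of liver events, and the qualifiers are there. Table 2-7 is a separate numeric laboratory summary.
- *Paced tracings must be removed from the QTcF counts.* Paced patients can enter, but the documents give neither their number nor their QTcF values, and the central reading rules for ECGs are not shown. Conditioning on baseline already removes anyone whose paced QTcF was above the threshold at entry.

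**Conclusion.** The point holds for the four isolated-ALP rows of Table 2-7 and for QTcF above 480 and 500 msec. Those rows count pre-existing and new abnormalities together. The ALT/AST and bilirubin rows are affected only through unconfirmed values or rises between Visit 1 and randomization.

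The effect is inflated counts in every arm and a diluted ratio: 3.0 shown as 1.66 or 1.32 at 2% or 5% carry-over. It would be wrong to infer an expected bias against LIK066 or any other arm, and the risk difference stays between 1.9 and 2.0 points in those two cases. In small arms, chance imbalance at entry can still make a single table look uneven.

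The size rests on assumed carry-over and assumed new-onset risks. The arm sizes of 62 and 124 are the planned ones; the SAP serves an abbreviated report after early termination, so the actual numbers may differ. No primary endpoint or error rate is involved. This is a cheap improvement to safety reporting.

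**What to change.** In SAP 2.6.2.6, report the Table 2-7 criteria, chiefly the isolated-ALP rows, as newly occurring. Count a patient in a row only if the baseline value did not already meet that row's criterion, use the patients not meeting it at baseline as the denominator, and print the number meeting it at baseline beside it. In SAP 2.6.2.5, do the same for QTcF above 480 and above 500 msec.

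Because each row is conditioned separately, a patient who enters above 1.5 × ULN and later exceeds 3 × ULN still counts as new in the >3 row.

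This is consistent with the rest of the SAP, which already restricts adverse events to those starting on or after the first dose and ties some PR and QRS rows to change from baseline. It needs no new data and changes no entry or clinical rule. The cost is SAP wording, a small programming change and slightly smaller denominators: at an assumed 5%, about 59 instead of 62 (62 × 0.95 = 58.9) and 118 instead of 124 (124 × 0.95 = 117.8).
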